## 2.3. Hypotheses

### Primary Hypotheses

1. Post-treatment subjective scores of comfort (VAS scale) for anesthetized eyes are superior to eyes that received the placebo for at least one of the ocular regions (upper lid margin, lower lid margin, or cornea).
2. Comfort change from pre-treatment for anesthetized eyes is superior to eyes that received the placebo for at least one of the ocular regions (upper lid margin, lower lid margin, or cornea).
3. Post-treatment subjective scores of comfort (VAS scale) for anesthetized eyes are equivalent to 5-minute post lens application levels in the morning for at least one of the ocular regions (upper lid margin, lower lid margin, or cornea). An equivalence margin of 10 points will be used.

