## **5. TEST ARTICLE ALLOCATION AND MASKING**

### **5.1. Test Article Allocation**

An ocular surface region (upper lid margin, lower lid margin or cornea) will be randomly allocated to each visit and a treatment (anesthesia or placebo) will be randomly allocated to each eye using a randomization scheme supplied by the study biostatistician. A single ocular region will be investigated at each visit and a single treatment will be applied to each eye at each visit. The clinical site will follow the randomization scheme provided and will complete enrollment according to the randomization list and will not pre-select or assign subjects. The assignment of the subjects must be performed at Visit 1. The following must have occurred prior to randomization:

- Informed consent has been obtained
- Subject meets all the inclusion / exclusion criteria
- Subject history and baseline information has been collected

The randomization scheme will be generated using the PROC PLAN procedure from the SAS Software Version 9.4 or higher (SAS Institute, Cary, NC).

The regions (upper lid margin, lower lid margin, or cornea) will be treated in a bilateral and random fashion using a Williams design with 3 regions and 3 periods. Each subject will be randomly assigned to one of six unique sequences (U/L/C, L/C/U, C/U/L, C/L/U, U/C/L, L/U/C). For each region within a sequence, the two treatments will be randomly assigned to the left and right eye (anesthesia left eye/placebo right eye or placebo left eye/anesthesia left eye).

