## 14.2. Sample Size Justification

The plan is to enroll 20 subjects with a target of 15 subjects to complete the study. This is a pilot study and the sample size was not based on any empirical power calculation.

The tables below, provided using the POWER procedure in SAS 9.4, summarizes statistical power based on the following assumptions:

- Testing for superiority with 0 VAS points and equivalence with +/- 10 VAS points
- True difference for superiority: 5, 7.5, 10 points and for equivalence: -5, 0, -5 points
- Estimated standard deviations of 15 and 20 points
- Intraclass correlations of 0.4, 0.6, and 0.8
- Two-sided type I error rate of 0.05
- 15 subjects successfully complete the study

Table 3: Power Analysis for the Primary Hypothesis (Superiority)

Difference (Test-Control)	Estimated Standard Deviation	Intraclass Correlation		
		0.4	0.6	0.8
5.0	15	0.300	0.393	0.617
5.0	20	0.211	0.269	0.425
7.5	15	0.515	0.661	0.897
7.5	20	0.351	0.460	0.705
10.0	15	0.724	0.864	0.987
10.0	20	0.515	0.661	0.897

The study is appropriately powered (power above 80%) to show superiority of anesthetized eyes over eyes that received the placebo when the difference in VAS comfort is at least 7.5 points and the intraclass correlation is at least 0.8.

Table 4: Power Analysis for the Primary Hypothesis (Equivalence)

Difference (Test-Control)	Estimated Standard Deviation	Intraclass Correlation		
		0.4	0.6	0.8
-5.0	15	0.259	0.386	0.617
-5.0	20	0.081	0.202	0.422
0.0	15	0.453	0.728	0.974

Difference (Test-Control)	Estimated Standard Deviation	Intraclass Correlation		
		0.4	0.6	0.8
0.0	20	0.117	0.334	0.794
5.0	15	0.259	0.386	0.617
5.0	20	0.081	0.202	0.422

The study is appropriately powered (power above 80%) to show equivalence between comfort scores at post-treatment and 5-minute post-application when there is no difference (0 VAS points) and the intraclass correlation is at least 0.8.

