### 14.5. Primary Analysis

#### VAS Comfort

VAS Comfort score at 5 and 10 minutes post treatment will be analyzed separately using a linear mixed model. The model will include the following experimental design factors: treatment, sequence of treatment, region, sequence of region, period, time event, and first-order carryover as fixed effects. Baseline characteristics such as age and gender may be included as covariates when appropriate. The covariance between residual errors for the same subject across periods will be modeled using one of the following covariance structures: Compound Symmetry (CS) or Unstructured (UN). The covariance structure that returns the lowest Akaike Information Criteria Corrected (AICC) will be selected as the structure that best fits the data. The Kenward and Roger method will be used for the calculation of denominator degrees of freedom.

The null and alternative hypothesis for superiority of anesthetized eyes compared to eyes that received the placebo with respect to VAS comfort at post treatment, where  $\mu_A - \mu_P$  is the difference in VAS comfort between anesthesia and placebo treatments, is as follows:

$$\begin{aligned}H_0: \mu_A - \mu_P &\leq 0 \\H_A: \mu_A - \mu_P &> 0\end{aligned}$$

The hypothesis will be tested via corresponding two-sided 95% confidence interval for least-squares mean difference (anesthesia minus placebo) of VAS comfort. Superiority will be concluded if the lower limit is greater than 0 for at least one of the three ocular regions (upper lid margin, lower lid margin, or cornea).

The null and alternative hypothesis for equivalence of VAS comfort scores at post-treatment and 5-minutes post-application, where  $\mu_1 - \mu_2$  is the difference in VAS comfort score between post-treatment and 5-minutes post-application, is as follows:

$$\begin{aligned}H_0: |\mu_1 - \mu_2| &\geq 10 \\H_A: |\mu_1 - \mu_2| &< 10\end{aligned}$$

The hypothesis will be tested via corresponding two-sided 95% confidence interval for least-squares mean difference (post treatment minus post application) in VAS comfort score. Equivalence will be concluded if the upper limit is less than 10 and the lower limit is greater than  $-10$ .

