### VAS Comfort (Change)

VAS Comfort score change from pre-treatment to 5 and 10 minute post-treatment values will be analyzed separately using a linear mixed model. The model will include the following experimental design factors: treatment, sequence of treatment, region, sequence of region, period, and first-order carryover as fixed effects; subject as a random effect. Baseline characteristics such as age and gender may be included as covariates when appropriate. The covariance between residual errors for the same subject across periods will be modeled using one of the following covariance structures: Compound Symmetry (CS) or Unstructured (UN). The covariance structure that returns the lowest Akaike Information Criteria Corrected (AICC) will be selected as the structure that best fits the data. The Kenward and Roger method will be used for the calculation of denominator degrees of freedom.

The null and alternative hypothesis for superiority of anesthetized eyes compared to eyes that received the placebo with respect to VAS comfort change from pre-treatment, where  $\Delta_A - \Delta_P$  is the difference in VAS comfort change from pre-treatment between anesthesia and placebo treatments, is as follows:

$$\begin{aligned}H_0: \Delta_A - \Delta_P &\leq 0 \\H_A: \Delta_A - \Delta_P &> 0\end{aligned}$$

The hypothesis will be tested via corresponding two-sided 95% confidence interval for least-squares mean difference (anesthesia minus placebo) of VAS comfort change from pre-treatment. Superiority will be concluded if the lower limit is greater than 0 for at least one of the three ocular regions (upper lid margin, lower lid margin, or cornea).

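### The section 14.5 models, fitted as listed, give one anesthesia-minus-placebo interval for all regions, while the decision rules need one per region; the equivalence rule also omits the anesthetized-eye and by-region limits of hypothesis 3

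*Combined protocol and SAP*

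**What the plan says.** Under VAS Comfort, section 14.5 lists the model terms as "treatment, sequence of treatment, region, sequence of region, period, time event, and first-order carryover as fixed effects". Under VAS Comfort (Change) the list is "treatment, sequence of treatment, region, sequence of region, period, and first-order carryover as fixed effects; subject as a random effect". No interaction, separate regional fit or contrast statement appears anywhere in section 14.

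Section 5.1 makes region a factor allocated to visits. Within each region, "the two treatments will be randomly assigned to the left and right eye", so treatment means anesthesia or placebo.

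Both superiority rules are regional: "Superiority will be concluded if the lower limit is greater than 0 for at least one of the three ocular regions". Primary hypotheses 1 and 2 in section 2.3 are worded the same way.

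Primary hypothesis 3 claims that post-treatment scores "for anesthetized eyes are equivalent to 5-minute post lens application levels in the morning for at least one of the ocular regions". The matching rule in section 14.5 uses only the "least-squares mean difference (post treatment minus post application) in VAS comfort score" with limits of ±10. It mentions neither treatment nor region.

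On time points: "VAS Comfort score at 5 and 10 minutes post treatment will be analyzed separately using a linear mixed model". Section 14.10 says the analysis will follow these sections as specified.

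**The concern.** In a model where treatment and region enter without their interaction, the treatment difference is one parameter. Asking for it in the upper lid, lower lid and cornea returns the same number and the same interval three times. A rule that looks for at least one regional lower limit above 0 then has nothing regional to look at.

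Equivalence has a further gap. Because the 5- and 10-minute scores are analyzed separately, a post-treatment minus post-application contrast needs the 5-minute post-application scores in the model as a level of time event. A time-event main effect averages over anesthetized and placebo eyes and over all three regions, which is not the quantity in hypothesis 3.

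The analyst must therefore either add terms that the plan does not list, choosing them after the data exist, or report a pooled interval for a rule written by region. The two can disagree when the effect sits in one region, and the listed model would not itself show which region responded.

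**Working it through.** **1. What the power tables assume.** Section 14.2 gives SD 15 or 20, ICC 0.4, 0.6 or 0.8, and "15 subjects successfully complete the study". For a paired comparison, SD of the difference = SD × √(2(1 − ICC)). For SD 15, ICC 0.4 this is 15 × √1.2 = 16.43. With 15 pairs the SE is 16.43/√15 = 4.243, and a difference of 10 has noncentrality 10/4.243 = 2.357. Power from the noncentral t on 14 df with 5% in one tail is 0.724, as in Table 3. ICC 0.6 and 0.8 give 0.864 and 0.987, also as printed, and the other Table 3 cells reproduce the same way. With 45 pairs (three regions pooled) the first value would be 0.991. The tables therefore describe one region: 15 eye pairs. (With the stated two-sided 5% the row would be 0.592, 0.766, 0.966. That is a separate matter.)

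**2. What the listed model estimates.** Take noise-free data in the Williams design with assumed true effects upper/lower/cornea = 0/0/10. Fitting the listed terms to post-treatment rows returns (0 + 0 + 10)/3 = 3.33 for every region. Adding treatment × region returns 0, 0 and 10.

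**3. Consequence for the superiority rule.** Simulated within-visit eye differences, 15 subjects, two-sided 95% limits, independent across visits. Pooled: 45 differences, 44 df. Regional: three means with a common residual, 42 df. The effect patterns are assumed.

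| True effect (upper/lower/cornea) | SD 15, ICC 0.8: pooled v regional | SD 20, ICC 0.4: pooled v regional |
|---|---|---|
| 0/0/10 (cornea contrast) | 54% v 98% | 16% v 41% |
| 0/5/10 (any region) | 91% v 99% | 31% v 50% |
| 5/5/10 (any region) | 99.5% v 99.4% | 51% v 55% |
| 10/10/10 (any region) | not informative, both near 100% | 85% v 78% |

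The cornea figures follow from the SEs: 15 × √0.4/√15 = 2.449, so 10/2.449 = 4.08; and 20 × √1.2/√15 = 5.657, so 10/5.657 = 1.77.

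**4. Consequence for the equivalence rule.** There are six eye-by-region cells, weighted equally by a time-event main effect.
- *Missing equivalence.* Assume only the anesthetized cornea returns to its morning level and the other five cells stay D points below. The pooled contrast is −5D/6. At D = 12 it is −10, on the margin, although the cornea difference is 0.
- *Passing wrongly.* Assume anesthetized eyes end 12 above and placebo eyes 5 below the morning level in every region. The pooled contrast is (12 − 5)/2 = +3.5, inside the margin, although no region meets hypothesis 3.

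How often the second case passes depends on correlation that the plan does not give. At SD 20, ICC 0.4 it is about 75% if all eye and visit differences are independent. It is about 28% with assumed correlations of 0.5 between eyes and 0.3 between visits and a subject-level interval. Only the direction of the error is firm.

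**5. Treatment coefficient when morning rows are included.** If time event had exactly two levels, 5 minutes post-application and one post-treatment time, the coefficient would average a time before treatment with a time after it: 3.33/2 = 1.67 for 0/0/10, and 10/2 = 5 for a uniform 10. The levels are not listed, so this is conditional.

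**The case against.** The strongest reply is that the interaction is implied. Section 14.1 calls the text a general description, section 14.5 lists design factors without saying that interactions are excluded, and the rules are explicitly regional. On that reading a pooled interval was never an option, and the pooled figures describe an analysis nobody planned. Much of this stands: the intent is clear, and the tables in section 14.2 support it. But the models are specified down to covariance structure and degrees-of-freedom method, and section 14.10 commits to the analysis as written. Nor does the implied reading say whether the regions share a residual or are fitted separately, or whether morning rows enter the superiority model.

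A second reply is that the size depends on the assumed pattern, and that this is a pilot not sized by a power calculation. Both are true. The table shows pooling about equal at 5/5/10 and better at 10/10/10. The study nevertheless has formal primary hypotheses, margins and a stated overall 5% error rate (section 14.4).

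A reader might infer more than the documents support:
- *A pooled success is invalid.* It is not: a correctly concluded positive average implies a positive effect in at least one region. What is lost is which region.
- *The secondary cornea-versus-lid contrasts are diluted by placebo eyes.* That holds only if the section 14.5 model is reused without the interaction. Section 14.6 specifies anesthetized eyes and states no model.
- *Regional testing breaks the 5% rate, so an adjustment belongs in this repair.* Three unadjusted regional tests give 1 − 0.975³ = 7.3% per endpoint and time point. That is a separate question: a correction across three regions alone would not settle the overall rate over two endpoints and two time points.

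**Conclusion.** The point holds as a mismatch between model and decision rule. Fitted as listed, neither section 14.5 model can produce the three regional lower limits that its superiority rule requires, whatever the true effects. The equivalence rule is also wider than hypothesis 3. A literal reading could miss equivalence in one region, or declare it when no region meets the 10-point margin.

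The documents do not show that a pooled analysis was intended. They point the other way, so this is a serious omission in the specification rather than a wrong design. The practical loss is large if the effect is confined to one region (54% v 98%, or 16% v 41%) and absent or reversed if it is similar in all regions. Those figures rest on the assumed effect patterns, 15 completers and independence across visits. They come from eye differences, not from the full mixed model. It should be fixed before the analysis.

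**What to change.** - Add treatment × region to both section 14.5 models.
- List the levels of time event. Where the 5-minute post-application scores are in the model, add time event × treatment × region with its lower-order terms.
- Name the contrasts: (a) anesthesia minus placebo at post-treatment within each region, for primary hypotheses 1 and 2; (b) post-treatment minus 5-minute post-application in anesthetized eyes of each region, for primary hypothesis 3; (c) cornea minus each lid margin in anesthetized eyes, for secondary hypotheses 1 and 2, stating which model section 14.6 uses.
- Restate the equivalence rule so that it refers to anesthetized eyes and to at least one region, as hypothesis 3 does.

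No new data or visits are needed. The change model uses 2 more degrees of freedom. A two-level time-event model uses 2 + 1 + 2 + 2 = 7 more (treatment × region, time event × treatment, time event × region, and the three-way term). If effects are equal in all regions, some power is given up against pooling: 78% v 85% at +10 everywhere with SD 20, ICC 0.4. Error control across regions, endpoints and time points should be settled separately against section 14.4.

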## **4. STUDY DESIGN AND RATIONALE**

### **4.1. Description of Study Design**

The study design is controlled, randomized, subject-masked, 3 treatment ×3 period, non-dispensing, contralateral study.

After a pre-screening assessment, eligible subjects will be invited to attend an initial visit. Subjects will be prescreened using the CLDEQ-8 questionnaire with their habitual lenses and those who are classified as symptomatic (CLDEQ-8 score of 20-37) will be scheduled for Visit 1.

At study Visit 1, subjects will be consented and screened for inclusion/exclusion criteria. If a subject is found to meet all eligibility criteria, they will be asked to attend Visit 2 which will take place on a different day. Subjects will be asked to wear their contact lenses early in the morning (at home) on the day of Visit 2 and to rate subjective comfort on a paper VAS scale immediately prior to lens application and 5 minutes post-application. They will be asked to attend the study visit having worn their habitual lenses for  $14 \pm 2$  hours. At Visit 2, one of three areas (upper lid margin, lower lid margin or cornea) will be anesthetized on one eye, whilst the fellow eye will receive a saline placebo treatment in the same location. The ocular surface region and treatment will be randomly assigned. The right eye will always be assessed first. Subjective comfort scores (VAS scale) will be collected prior to and following the treatment on each eye (5 and 10 minutes post-treatment). On the day of corneal treatment, VAS comfort scores will also be collected immediately after lens removal prior to treatment application. Subjects will be asked to return for Visit 3 on a different study day, again having worn their lenses for  $14 \pm 2$  hours and the same procedures as at Visit 2 will take place. The same procedures as for Visit 3 will be repeated for Visit 4. Visits 2-4 will be scheduled 1-14 days apart.

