Visit 2-4 (in clinic after 14 ± 2 hours of lens wear)			
Step	Procedure	Details	
2.4	Adverse Events and Concomitant Medications Review	Review any changes to the subject's medical history or concomitant medications from the previous study visit. Record any changes, and any adverse events.	
2.5	Wearing Time	Record the wearing time since application and comfortable wearing time.	
2.6	Subject Reported Ocular Symptoms	Subjects will respond to a verbal open-ended symptoms questionnaire.	
2.7	Collection of VAS scale	The investigator will collect the comfort VAS scales and will enter the scores on the database.  If subjects have not completed the VAS scales, the visit can be rescheduled to a different day for a maximum of two further occasions.	
2.8	Entrance Visual Acuity	Record the distance high contrast visual acuity to the nearest letter (OD and OS) with their habitual contact lenses.	Eurolens Research SOP #12a
2.9	Slit Lamp Biomicroscopy (white light only)	Efron Slit Lamp Classification Scale will be used to grade the findings.  If any of these slit lamp findings are Grade 3 or higher, it will be recorded as an Adverse Event.	Eurolens Research SOP #13
2.10	Subjective Lens Fit Assessment	Lens fit will be recorded according to a -2 to +2 integer scale for each of the following criteria:  Horizontal centration: -2 = Extremely Nasal -1 = Slightly Nasal 0 = Optimum +1 = Slightly Temporal +2 = Extremely Temporal  Vertical centration: -2 = Extremely Superior -1 = Slightly Superior 0 = Optimum +1 = Slightly Inferior +2 = Extremely Inferior  Coverage: -2 = Extremely Inadequate -1 = Slightly Inadequate 0 = Optimum	

		
+1 = Slightly Excessive +2 = Extremely Excessive
 
Movement -2 = Extremely Inadequate -1 = Slightly Inadequate 0 = Optimum +1 = Slightly Excessive +2 = Extremely Excessive
	
2.11	Subjective comfort	Subjective comfort scores (vertical VAS scale) will be collected for each eye.	██████████

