2.12	Right eye Application of topical treatment	
One ocular region (upper lid margin, lower lid margin or cornea) of the right eye will be anesthetized or will receive a saline placebo treatment, based on the randomization scheme.
 
The procedures will take place with the subject's lenses in situ when the lid margins are treated. When the cornea is anesthetized, the subject's habitual lens will be removed and immediately dosed with the anesthetic as outlined in SOP #54. The lens will not be spun to removed excess liquid and will not be soaked in any solution prior to re-insertion. The dosing/re-application procedure should take place as quickly as possible to avoid the lens from dehydrating excessively.
 
If any problems with the application of the treatment occur, subjects are eligible to repeat the visit on another day only once.
	Eurolens Research SOP #54
2.13	Right eye Subjective comfort	
Subjective comfort scores (vertical VAS scale) will be collected for the right eye after 5 and 10 minutes post-treatment.
 
For the cornea, the contact lens is removed and then reapplied as part of the treatment application procedures. Comfort scores will also be collected immediately (ideally within 30 seconds) after lens removal prior to treatment application.
	██████████
2.14	Left eye Application of topical treatment	The same ocular region (upper lid margin, lower lid margin or cornea) of the left eye will be anesthetized or will receive a saline placebo treatment, based on the randomization scheme.	Eurolens Research SOP #54

		
The procedures will take place with the subject's lenses in situ when the lid margins are treated. When the cornea is anesthetized, the subject's habitual lens will be removed and immediately dosed with the anesthetic as outlined in SOP #54. The lens will not be spun to removed excess liquid and will not be soaked in any solution prior to re-insertion. The dosing/re-application procedure should take place as quickly as possible to avoid the lens from dehydrating excessively.
 
If any problems with the application of the treatment occur, subjects are eligible to repeat the visit on another day only once.
	

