2.15	Left Subjective comfort	
Subjective comfort scores (vertical VAS scale) will be collected for the left eye after 5 and 10 minutes post-treatment.
 
For the cornea, the contact lens is removed and then reapplied as part of the treatment application procedures. Comfort scores will also be collected immediately (ideally within 30 seconds) after lens removal prior to treatment application.
	██████████
2.16	Contact lens removal	Contact lenses will be removed and discarded.	
2.17	Exit Slit Lamp Biomicroscopy (Visits 2-3 only)	
Efron Slit Lamp Classification Scale will be used to grade the findings.
 
Adverse events shall be documented and followed to resolution.
 
If the clearance of the fluorescein needs to be expedited, preservative-free rewetting drops or saline may be instilled.
	Eurolens Research SOP #13
2.18	Exit VA (Visits 2-3 only)	Record subjects' distance high contrast visual acuity to the nearest letter (OD and OS) with their habitual spectacle correction in place (or unaided if applicable).	Eurolens Research SOP # 12a
2.19	End of Visit (Visits 2-3)	Subject discharged and asked to return for next visit. Subjects can leave wearing spectacles or unaided as determined by the investigator.	

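### Treatment is randomized to eye and the right eye always goes first, but neither primary model in 14.5 has an eye/order term: this costs precision and allows chance shifts, without systematic bias

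*Combined protocol and SAP*

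**What the plan says.** **Allocation.** Section 5.1: "For each region within a sequence, the two treatments will be randomly assigned to the left and right eye". The list comes from the study biostatistician through PROC PLAN. Nothing says whether left and right are balanced within a region.

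**Order.** Section 4.1: "The right eye will always be assessed first". Section 7.2 gives the sequence at Visits 2-4:
- Step 2.11, before any treatment: "Subjective comfort scores (vertical VAS scale) will be collected for each eye".
- Steps 2.12-2.13, right eye treated, then: "Subjective comfort scores (vertical VAS scale) will be collected for the right eye after 5 and 10 minutes post-treatment".
- Steps 2.14-2.15, left eye treated, then: "Subjective comfort scores (vertical VAS scale) will be collected for the left eye after 5 and 10 minutes post-treatment".

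**Models.** In section 14.5 the post-treatment score model has "treatment, sequence of treatment, region, sequence of region, period, time event, and first-order carryover as fixed effects". The change model has "treatment, sequence of treatment, region, sequence of region, period, and first-order carryover as fixed effects; subject as a random effect". The covariates named as optional in both are age and gender.

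**The concern.** The primary superiority contrast compares fellow eyes at the same visit. Eye is the unit to which treatment is assigned, and it is completely tied to order. In the sequence listed, the left eye's post-treatment scores come at least about 10 minutes later than the right eye's, after a long day of lens wear and with the right eye already treated. The design itself therefore makes some right-left difference plausible.

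No listed term absorbs such a difference. Age and gender are constant within a subject, and period refers to the visit. With a target of 15 completers, what is at stake is avoidable loss of power, and a regional estimate that moves with the accident of which eyes received anesthesia. Superiority needs only one of three regions, so an estimate moved by imbalance in a single region matters.

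**Working it through.** **Inputs.** From section 14.2: 15 completers, SD 15 or 20, ICC 0.4, 0.6 or 0.8, effect 7.5 points, two-sided 0.05. From section 14.5: superiority is judged by a two-sided 95% interval. The right-left/order difference E is not in the documents, so E = 5 is assumed, with 3 to 8 as the range.

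**1. The plan's own figure.** Table 3 gives power 0.897 at 7.5 points, SD 15, ICC 0.8.
- SD of the paired difference = 15 × √(2 × (1 − 0.8)) = 9.49. SE = 9.49/√15 = 2.45. Noncentrality = 7.5/2.45 = 3.06, with 14 df.
- One-sided 0.05 gives 0.897, and all 18 cells of Table 3 reproduce that way. Two-sided 0.05, the stated level, gives 0.812.

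That mismatch is a separate matter. Everything below uses the two-sided 95% interval of section 14.5.

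**2. Do the existing terms cover eye?** *Sequence of treatment* is not defined. If it means which eye receives anesthesia, eye equals the treatment-by-sequence interaction. Adding eye to intercept, treatment and sequence raises the model rank from 3 to 4, so the main effects listed do not adjust for it.

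**3. Effect on the estimate.** For one region write D = τ + sE + e, where D is anesthesia minus placebo, and s = +1 if the right eye is anesthetized and −1 if the left. The mean of D is τ + E(nR − nL)/n.
- Over the randomization the shift averages zero. In simulation at a true effect of 7.5, the mean estimate is 7.5 with or without the eye term.
- For a given split the shift is E/15 at 8:7, E/3 at 10:5 and 7E/15 at 11:4. At E = 5 that is 0.33, 1.67 and 2.33 points, against an SE of 2.45.
- If eyes are assigned by independent coin flips (an assumption), a split of 10:5 or worse in either direction has probability 2 × P(X ≤ 5 | 15, 0.5) = 0.30 per region. For at least one of three regions it is 1 − (1 − 0.302)³ = 0.66.

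**4. Effect on noise.** Near balance, leaving eye out adds about E² to the variance of D. At SD 15 and ICC 0.8 that takes 90 to about 115 for E = 5. At SD 20 and ICC 0.4 it takes 480 to about 505, which hardly matters.

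**5. Type I error** (SD 15, ICC 0.8, E = 5, no eye term). The upper-tail rate is about 6.0% given a 10:5 split in the direction of the difference, 0.2% at the mirror split, 1.8% at 8:7, and 2.5% averaged over the randomization.

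**6. Power at 7.5 points**, simulated with 15 subjects × 3 regions, coin-flip eye assignment and residual pooled over regions (42 df without the term, 41 with), E = 5:

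| SD | ICC | Without eye term | With eye term |
|---|---|---|---|
| 15 | 0.8 | 0.75 | 0.84 |
| 15 | 0.6 | 0.51 | 0.55 |
| 20 | 0.8 | 0.55 | 0.60 |
| 20 | 0.4 | 0.24 | 0.25 |

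The other two planning cells (SD 15/ICC 0.4 and SD 20/ICC 0.6) gain 3 points or less. At SD 15 and ICC 0.8, E = 3 gives 0.81 against 0.84, E = 8 gives 0.62 against 0.84, and E = 0 gives 0.85 against 0.84. With each region analyzed alone, E = 5 gives 0.71-0.73 against 0.78-0.81, and E = 0 gives 0.815 against 0.78-0.81.

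**7. Change model.** Both eyes are scored at step 2.11 before either is treated, so a stable right-left difference cancels in the change score. Only an order effect is left, and E must be read that way there.

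**8. What the term cannot do.** Suppose anesthesia of the right eye moves the rating of the placebo left eye by c. Mean D is then τ + E − c when the right eye is anesthetized and τ − E when the left is. The eye-adjusted average is τ − c/2, so half of c remains.

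**The case against.** The strongest reply is that randomization to eye already protects the comparison: the estimator is unbiased and overall type I error stays at its nominal level. This is a pilot whose size did not come from a power calculation, and section 14.1 allows further exploratory analysis. The randomization list may be balanced, and *sequence of treatment* may have been meant as first or second eye, which would be the missing term.

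Much of this stands. A reader might infer that every right-left difference passes straight into the anesthesia-placebo contrast, or that the false-positive rate rises to about 6%. The documents support neither: the expected shift is zero, and 6% is the rate after one unfavorable split, offset by 0.2% at its mirror image. A reader might also infer that the lens-removal analysis needs the same term. It compares two times with both eyes scored at each, so an eye main effect leaves that contrast unchanged.

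Two parts do not stand. Balance would remove the shift but not the noise: with an 8:7 split and each region alone, power at E = 5 is 0.73 without the term and 0.81 with it (SD 15, ICC 0.8). And the plan does not define *sequence of treatment* per eye, so it cannot be taken as the eye term.

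**Conclusion.** The point holds as one of precision and of chance shifts within a region. Both primary models omit the one within-visit design factor other than treatment, and no listed term clearly replaces it. There is no bias on average and no inflation of unconditional type I error.

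The gain from adding the term rests on an assumed difference. At 5 points it runs from about 9 percentage points of power (SD 15, ICC 0.8) to under 1 (SD 20, ICC 0.4). In the change model it depends on an order effect alone. The imbalance probabilities assume unrestricted eye assignment, which the protocol neither states nor rules out. This is a cheap improvement worth making before the analysis; it does not invalidate the planned one.

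**What to change.** - Add eye (right/first versus left/second) as a within-subject fixed effect to both primary models in section 14.5. Laterality and order cannot be separated in this design, but one term covers both.
- Define *sequence of treatment*. It need not be removed for this fix.
- State in section 5.1 whether eye assignment is balanced within region, and correct the second assignment in its closing parenthesis, which names the left eye for both treatments.
- Report treatment-by-eye as supportive only. It can point to an effect of right-eye anesthesia on the left-eye rating, which the eye term does not remove.

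Cost: one degree of freedom. If the eyes do not differ, about 1 percentage point of power is lost with a pooled residual, or up to about 3 if each region is analyzed alone. No study procedure changes.
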